### 3.1.2. Psoriasis Multiple Dose Cohorts

In the multiple dose psoriasis subject cohorts, approximately 42 subjects will be enrolled with approximately 14 subjects receiving placebo, and approximately 28 subjects receiving one of two possible PF-06826647 dose levels, for 28 days. PF-06826647 dose range for the psoriasis cohorts will be selected based on emerging PK, CCI and safety data from the healthy subjects SAD/MAD periods. Refer to Protocol Section 1.3.4.1 for psoriasis dose selection rationale. QD dosing is planned for psoriasis subjects, however, daily dosing regimen (eg, QD, BID) may be adjusted based on emerging PK data from the SAD/MAD periods. Psoriasis subjects who discontinue early from the trial may be replaced at the discretion of the sponsor. PF-06826647 dose level in psoriasis may be adjusted based on emerging clinical data from the planned interim analysis, at the discretion of the Sponsor. Any potential PF-06826647 dose adjustments for psoriasis Cohort 2 will be applied after review of PK, CC and safety data up to 28 day in the 400 mg psoriasis cohort.

Initiation of dosing in psoriasis subjects will be based on available safety data from the healthy subject MAD period. Psoriasis subjects enrolled into the multiple dosing period will receive PF-06826647 or placebo (QD) for 28 days, with a 56 day follow-up period post last dose. Doses will be selected based on emerging PK, PD and safety data from the study (not to exceed  $C_{max}$  and  $AUC_{0-24}$  limits of 1870 ng/mL and 16,600 ng·h/mL, respectively). Dosing in psoriasis subjects will commence if adequate safety is demonstrated in healthy subjects participating in the MAD period at the equivalent dose level. At a minimum, 10 day safety and PK data from at least 6 healthy subjects (with at least one subject on placebo) receiving the equivalent QD dose level will be reviewed to confirm that a given PF-06826647 dose is safe and well tolerated before administering PF-06826647 to psoriasis subjects. Subjects will be housed through Day 28 of the multiple dosing period, discharged on Day 28, to return for outpatient visits on the mornings of Days 35 ( $\pm 3$  days), 42 ( $\pm 3$  days), 56 ( $\pm 3$  days) and 84 ( $\pm 3$  days)(end of study). The 28 day treatment duration is supported by preclinical toxicology data and will facilitate assessment of CCI, as well as assessment of clinical endpoints (eg, PASI).

**Figure 1. Study Schema**

Numbers 1 – 8 refer to subject cohorts. Subjects completing the SAD period will continue into the MAD period when applicable, after protocol defined washout and follow up.

\* Cohorts 7 and 8 are optional single dose cohorts that may be conducted at discretion of Sponsor and based on emerging PK data. If conducted, the dose and meal condition will be decided based on emerging PK, PD, and safety data from the multiple ascending dose period of the trial.

\*\* Cohort 9 is an optional cohort for assessment of twice daily (BID) PF-06826647 dosing. BID dose level will be determined based on emerging PK, PD, safety and tolerability data. The planned PF-06826647 dose level to be administered in the BID cohort is 200 mg twice daily (total daily dose of 400 mg).

\*\*\* Based on interim analysis results from 400 mg psoriasis cohort, the PF-06826647 dose level for psoriasis Cohort 2 may be adjusted. The maximum dose administered to psoriasis subjects will not be expected to exceed the exposure at the maximum tolerated dose in the healthy subject MAD period.

[figure not shown]
HVs = healthy volunteers

All cohorts are placebo controlled .

Note on optional Japanese subject cohort: if conducted, administration of PF-06826647 (or matching placebo) to Japanese subjects will occur once daily for 10 day duration, and subjects will follow the MAD period [schedule of activities](#).

**Figure 2. Legend for Figure 1**

SAD = Single ascending dose Period 1                      QD = once daily  
MAD= multiple ascending dose Period 2                      BID=twice daily

**3.2. Dose Escalation and Stopping Rules**

The following dose escalation rules apply to the single and multiple ascending dose healthy subject cohorts. Individual stopping rules for healthy subjects (SAD/MAD) and psoriasis subjects are also outlined below.

Dose-escalation stopping rules will be used to determine whether the maximal tolerated dose has been attained. Dose escalation may be stopped if it is determined that the limits of safety and/or tolerability have been reached. This decision will be made after a discussion takes place between the sponsor study team and the investigator. The sponsor study team may not overrule the investigator’s decision to stop dose escalation. If dose escalation is stopped because of any of these criteria, additional cohorts may receive the same or lower doses of the investigational product.

The dose escalation will be terminated based on the following criteria:

- If 50% or more of the subjects receiving active drug at a given dose level (but not subjects receiving placebo) develop similar clinically significant laboratory, electrocardiogram (ECG), or vital sign abnormalities as described below in [Section 3.3](#)), or severe adverse events (AEs) in the same organ class, indicating dose-limiting intolerance.
- Dosing will be paused for any serious adverse event (SAE) that occurs in a subject receiving active treatment until causality is fully assessed by the principal investigator (PI) and sponsor. Dosing may resume if the SAE is determined to be not drug-related

by the PI and sponsor. If the SAE is determined to be either drug-related or unknown, either dosing will cease or the SAE will be evaluated by the sponsor's protocol review committee (or similar review group), which is independent of the study team and investigators. If the protocol review committee determines that dosing may resume, a plan that mitigates risks to subjects with the resumption of dosing will be implemented. Such a plan could include a revision of inclusion/exclusion criteria, repeating or reducing the dose, or adding appropriate safety monitoring.

- It is determined that the limit of safety and/or tolerability has been reached. This decision will be made following discussions between the study team and the investigator.
- Other findings that, at the discretion of the study team and investigator, indicate that dose escalation should be halted.
- If, at any dose level, the average exposure reaches or exceeds the pharmacokinetic (PK) stopping limits based on free  $C_{max}$  and  $AUC_{0-24}$  values of 1870 ng/mL and 16,600 ng.h/mL, respectively.
- If, based on the observed data, the group mean maximum observed concentration ( $C_{max}$ ) or area under the curve (AUC) (based on total plasma concentration) of the next planned dose is projected to exceed the escalation limits, that dose will not be explored. Modified doses may be explored if they are not expected to exceed PK stopping criteria.

Progression to the next single dose level will occur if the last dose was well tolerated and after satisfactory review of the available safety and PK data. Minimum data required for dose escalation review includes 24 hour PK data, adverse event/serious adverse events, vital sign and ECG data, urinalysis, chemistry and hematology laboratory results through Day 3 in at least 6 subjects (with at least one subject on placebo) within a given dose cohort.

Initiation of the multiple ascending dose study will commence at the 10 mg dose level if adequate safety is demonstrated for single doses up to 30 mg. Similarly, the 30 mg dose level will not be initiated until the safety/tolerability has been established up to 100 mg single dose and a minimum of 10 days of safety data (vital sign and ECG data, urinalysis, chemistry, hematology, adverse event data) and 10 day PK data from the preceding multiple dose cohort from at least 6 subjects (with at least one subject on placebo). The remainder of the cohorts will follow a similar escalation paradigm (except for the highest MAD cohort dose level, which will be equal to or less than the maximum SAD dose level tested). Dosing in highest dose MAD cohort will commence if adequate safety is demonstrated in SAD cohort at the same or higher dose level and the projected exposure at steady state does not exceed NOAEL. Dose levels may be adjusted based on emerging PK data from this study, however, this escalation paradigm will still apply.

### 3.3. Individual Stopping Rules for the Healthy Subjects during the Single and Multiple Ascending Dose Periods

#### Adverse Events:

- Dosing will be discontinued for any treatment emergent serious adverse event (SAE) that occurs in a subject receiving active treatment unless the SAE is clearly unrelated to study drug (eg, subject is the victim of a motor vehicle accident).
- Serious infections, defined as any infection (viral, bacterial, and fungal) requiring parenteral antimicrobial therapy or hospitalization.

#### Laboratory, Vital Sign, and ECG Abnormalities:

Individual stopping rules will be based on repeated measures (single repeat preferably performed within 24 hours of initial result) of the parameters outlined below.

- Grade 3 lymphopenia ( $<500$  cells/mm^3).
- Grade 3 neutropenia ( $<1000$  cells/mm^3).
- Grade 3 ALT/AST ( $>5x$  upper limit of normal (ULN) when not accompanied by an increase in bilirubin).
- Grade 3 bilirubin ( $>2.0$  x ULN when not accompanied by an increase in ALT/AST).
- Changes in liver function tests that meet Hy's Law criteria.
- Serum creatinine  $\geq 1.5$  x ULN.

**Note:** An increase of  $\geq 0.3$  mg/dL (or  $\geq 26.5$   $\mu$ mol/L) in serum creatinine relative to subjects' own baseline measurement should trigger another assessment of SCr within 24-hours from awareness. See [Potential Cases of Acute Kidney Injury](#) for further guidance.

- Grade 2 Hemoglobin  $<10$  g/dL.
- Grade 2 Platelets  $<75,000$ /mm^3 or  $>750,000$ /mm^3.
- 12-lead ECG demonstrating QTc  $\geq 500$ ; or a QRS interval  $\geq 140$  msec or  $\geq 50\%$  increase from baseline; PR interval  $\geq 300$  msec or 25% increase over baseline when baseline  $>200$  msec.

Blood pressure or pulse rate measurements meeting criteria for individual stopping rules should be repeated at least twice, separated by at least 5 minutes, with the subject at rest, supine. If confirmed to be abnormal and confirmed to be clinically significant by investigator, dosing should be stopped and the blood pressure/pulse should be followed

periodically, as deemed appropriate by the investigator, until the blood pressure/pulse rate are returned to within normal limits or deemed acceptable by the investigator.

- Vital sign abnormalities:
  - Systolic blood pressure <90 mmHg or >160 mm Hg;
  - Diastolic blood pressure <50 mmHg or >100 mm Hg;
  - Pulse rate supine/sitting <36 or >120 beats per minute (bpm); standing <36 or >140 bpm.

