Vital signs: Supine single PR, BP and Oral Temperature i	X	X		X	X	X	X		X		X	X	X	X	X		X	X	X	X	X	X	X	X	X	X	X	X	X	X	X	X	X	
24 hr Urine Collection for CCI measurement, Creatinine Clearance, 6-β-Hydroxycortisol/cortisol ratio and Urine PK j	0-24 hr									0-24 hr																								
Study Treatment Administration		X									X	X	X	X	X		X																	
PK Blood Sampling k		X	X	X	X	X	X	X			X		X		X		X	X	X	X	X	X	X	X	X	X	X	X	X	X	X			
CCI																																		
Serious and non-serious adverse event monitoring	X	X									→	→	→	→	→		→	→	→	→	→	→	→	→	→	→	→	→	→	→	→	→	X	
Prior/Concomitant treatment	X	→									→	→	→	→	→		→									→	→	→	→	→	→			
CCI																																		

Abbreviations: →= ongoing/continuous event; BP = blood pressure; CCI [redacted]; CRU = clinical research unit; CCI [redacted]; ECG = electrocardiogram; CCI [redacted]; PK = Pharmacokinetics; PR = pulse rate; CCI [redacted]

- a. End of study procedures ( $\pm 3$  day).
- b. Prior to dosing on Day 1, confirm that safety labs, ECG, and vital sign results, contraception check and prior/concomitant treatments from Day -1 (or from Day 8 of SAD if obtained within 48 hours of MAD Day -1) meet eligibility requirements outlined in [Section 4.2](#). If labs, vitals, or ECG results are not within limits as outlined in [Section 4.2](#), the site will notify sponsor. PI and sponsor will make the determination as to whether or not to allow the subject to continue into the MAD period. If the out of range values meet individual stopping rules outlined in the protocol, the subject will not continue into the MAD period.
- c. See protocol [Section 4.6.4](#) (Contraception). Investigator will discuss appropriate contraception methods with male subjects.
- d. Subjects will reside in the clinical research unit until the morning of Day 14, returning on the morning of Day 28  $\pm 3$  days for the end of study procedures visit.
- e. Limited physical examination (at the discretion of the principle investigator, exam may be limited or full).
- f. Chemistry and hematology labs are collected following fasting period of at least 8 hours (on Day 10, fasting applies to hour 0 labs only).
- g. Lipid panel (Cholesterol, Triglycerides, HDL, and LDLc): Fasting requirement of at least 8 hours.
- h. ECGs will be collected in triplicate approximately 2-4 minutes apart on Days 1, 2, 4, 6, 8, 10 and Day 11. Single ECGs will be collected at all other specified visits.

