### 1.3.2. Preliminary Summary of Clinical Experience

As of March 25, 2018, the one, *on-going* clinical trial is the current study, C2501001. In this study, dosing of six single ascending dose cohorts and three multiple ascending dose cohorts has been completed, with 53 healthy adult subjects randomized and treated with PF-06826647 or placebo. To date, preliminary safety and PK data indicate that the stopping criteria, as outlined in Protocol [Section 3.3](#), have not been met.

There have been no serious adverse events (including death) reported. Based on preliminary review of data, all reported adverse events (AEs) have been of mild intensity.

Preliminary pharmacokinetic data from the 3, 10, 30, 100, 400, and 1600 mg dose levels in SAD are summarized in [Table 1](#). The results indicate that exposure (AUC and  $C_{max}$ ) is lower than predicted by GastroPlus simulations presented in [Table 3](#), therefore, the safety margin based on observed exposure is larger than what was initially expected. The increase in exposure appears to be less than proportional between 10 mg and 400 mg cohort and linear between 400 and 1600 mg. The preliminary PK data suggest longer terminal half-life at higher dose, possibly due to the biphasic concentration time profile and increased ability to measure the concentration for longer period at higher dose. The terminal half-life at 10 mg was approximately 6 hours whereas at 400 mg it was approximately 15 hours.

**Table 1. Preliminary Summary of Draft Plasma PK Parameters of PF-06826647 Following Single Oral Dose Administration of PF-06826647 in Healthy Subjects (Fasted)**

Single Dose (mg)	C max (ng/mL)	AUC 24 (ng.hr/mL)	AUC last (ng.hr/mL)	t 1/2 hr
3	8 (38)	40 (56)	40 (56)	NR
10	47 (35)	346 (64)	355 (67)	6 (33)
30	78 (34)	543 (49)	639 (58)	NR
100	167 (55)	1160 (55)	1378 (53)	NR
400	329 (28)	1933 (28)	2135 (26)	15 (33)
1600	1218 (25)	9321 (34)	9796 (34)	13 (56)

Geometric mean (%CV) for all except arithmetic mean (%CV) for t1/2; Abbreviations: %CV = percent coefficient of variation; NR = Not Reportable; AUC24= Area under the concentration-time curve from time zero to 24 hours post single dose; Cmax = Peak plasma concentration.

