At least 14 days (minimum wash-out period) will separate the beginning of the single and multiple dose periods (ie, at least 14 days will separate the single dose administered in the SAD and the first QD dose in the MAD); however, the minimum wash-out period may be adjusted based on emerging PK data. Based on the PK predictions and emerging PK data from this study, the currently planned starting dose in the MAD period is 30 mg (previously, a PF-06826647 starting dose of 10 mg was planned for the MAD period under the original protocol) is not expected to provide pharmacologically relevant exposure. In the multiple ascending dose (MAD) period, healthy subjects in Cohort 3 to Cohort 6 in Period 2 will receive doses of 30, 100, 400, or 1200 mg QD of PF-06826647 or placebo for 10 days (Day 1 through Day 10) with standard meal. The dose of Cohort 6 in MAD (Period 2) may be adjusted based on emerging data from earlier MAD cohorts in the trial. Subjects will be housed for the duration of the multiple dosing period, discharged on the morning of Day 14. Subjects will return for outpatient visits on morning of Day 17 for PK sample collection and Day 28 ( $\pm 3$  days) for end of study procedures. Based on emerging PK data, subject may be asked to return between Day 17 and Day 28 for an additional outpatient visit for PK sample

collection. The additional PK sample will allow characterization of terminal half-lives at higher dose cohorts.

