### 8.4. Special Situations

#### 8.4.1. Potential Cases of Drug-Induced Liver Injury

Humans exposed to a drug who show no sign of liver injury (as determined by elevations in transaminases) are termed “tolerators,” while those who show transient liver injury, but adapt are termed “adaptors.” In some subjects, transaminase elevations are a harbinger of a more serious potential outcome. These subjects fail to adapt and therefore are “susceptible” to progressive and serious liver injury, commonly referred to as drug-induced liver injury (DILI). Subjects who experience a transaminase elevation above 3 times the upper limit of normal ( $\times$  ULN) should be monitored more frequently to determine if they are an “adaptor” or are “susceptible.”

In the majority of DILI cases, elevations in aspartate aminotransferase (AST) and/or alanine aminotransferase (ALT) precede total bilirubin (TBili) elevations ( $>2 \times$  ULN) by several days or weeks. The increase in TBili typically occurs while AST/ALT is/are still elevated above  $3 \times$  ULN (ie, AST/ALT and TBili values will be elevated within the same lab sample). In rare instances, by the time TBili elevations are detected, AST/ALT values might have decreased. This occurrence is still regarded as a potential DILI. Therefore, abnormal elevations in either AST OR ALT in addition to TBili that meet the criteria outlined below are considered potential DILI (assessed per Hy’s law criteria) cases and should always be considered important medical events, even before all other possible causes of liver injury have been excluded.

The threshold of laboratory abnormalities for a potential DILI case depends on the subject’s individual baseline values and underlying conditions. Subjects who present with the following laboratory abnormalities should be evaluated further as potential DILI (Hy’s law) cases to definitively determine the etiology of the abnormal laboratory values:

- Subjects with AST/ALT and TBili baseline values within the normal range who subsequently present with AST **OR** ALT values  $>3 \times \text{ULN}$  AND a TBili value  $>2 \times \text{ULN}$  with no evidence of hemolysis and an alkaline phosphatase value  $<2 \times \text{ULN}$  or not available.
- For subjects with baseline AST **OR** ALT **OR** TBili values above the ULN, the following threshold values are used in the definition mentioned above, as needed, depending on which values are above the ULN at baseline:

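### In Section 3.3 a second abnormal liver test can switch off a mandatory stop for healthy subjects, and the Hy's law rule does not catch every case released

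*Protocol*

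**What the plan says.** Protocol Section 3.3 gives three laboratory liver stops for healthy subjects, each based on a repeated measurement:

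- ALT/AST above 5 times the "upper limit of normal (ULN) when not accompanied by an increase in bilirubin";
- bilirubin above 2.0 times "ULN when not accompanied by an increase in ALT/AST";
- liver test changes that meet Hy's law.

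Section 8.4.1 defines Hy's law for a subject with normal baseline values. ALT or AST must exceed 3 times ULN and total bilirubin 2 times ULN, "with no evidence of hemolysis and an alkaline phosphatase value" below 2 times ULN or not available. Neither document says what counts as an increase in the other test.

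Two other rules depend on Section 3.3. Footnote b of the multiple ascending dose (MAD) Schedule of Activities states: "If the out of range values meet individual stopping rules outlined in the protocol, the subject will not continue into the MAD period". For other out-of-range values the investigator and sponsor decide. Section 3.2 ends escalation if at least 50% of subjects on active drug at a dose level "develop similar clinically significant laboratory, electrocardiogram (ECG), or vital sign abnormalities as described below in" Section 3.3, or have severe adverse events in the same organ class.

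The psoriasis stops in Section 3.4 are AST or ALT above 2.5 times ULN and total bilirubin above 1.5 times ULN. Neither depends on the result of the other test.

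**The concern.** A stopping rule should not become more lenient as the findings get worse. Here each single-test stop lapses when the partner test is also raised. That is safe only if the combined rule takes over everywhere the single-test rules lapse, and the thresholds do not meet.

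Three automatic consequences can be lost:

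- the individual stop during the 10 days of MAD dosing;
- the absolute bar to entering MAD, which is the main effect after a single dose in the single ascending dose (SAD) period;
- the subject's contribution, as a laboratory abnormality, to the 50% escalation criterion.

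Section 1.3.2 reports that "dosing of six single ascending dose cohorts and three multiple ascending dose cohorts has been completed" in 53 subjects, with no stopping criterion met. The three completed MAD doses are 30, 100 and 400 mg QD. The plan is that Cohorts 3 to 6 "will receive doses of 30, 100, 400, or 1200 mg QD", so the cohort still to come is at 1200/400 = 3 times the highest completed MAD dose. Section 9.8 provides no external data monitoring committee.

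**Working it through.** The plan gives no figure to reproduce, so the check applies the rules themselves.

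**Inputs.** The three stops come from Section 3.3 and the Hy's law terms for a normal baseline from Section 8.4.1. All values are multiples of ULN.

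**Rule as written.** Stop if

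- ALT/AST >5 and bilirubin not increased, or
- bilirubin >2 and ALT/AST not increased, or
- ALT/AST >3 and bilirubin >2 and ALP <2 (or not available) and no hemolysis.

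**Assumption for the undefined word.** Reading A: increased means above 1 x ULN. Reading B: increased means the Hy's law cut-offs, ALT/AST >3 and bilirubin >2.

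**Classes.** ALT/AST (≤1, >1–3, >3–5, >5) by bilirubin (≤1, >1–2, >2) by ALP/hemolysis (ALP <2 and no hemolysis; ALP ≥2 or hemolysis) gives 4 × 3 × 2 = 24. Those with ALT/AST >5 number 3 × 2 = 6. Those with bilirubin >2 and ALT/AST ≤5 number another 3 × 2 = 6. So 12 classes cross a threshold.

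| ALT/AST | Bilirubin | ALP / hemolysis | Classes | Reading A | Reading B | Conditions deleted |
|---|---|---|---|---|---|---|
| >5 | ≤1 | either | 2 | stop | stop | stop |
| >5 | >1–2 | either | 2 | **none** | stop | stop |
| >5 | >2 | ALP <2, no hemolysis | 1 | stop | stop | stop |
| >5 | >2 | ALP ≥2 or hemolysis | 1 | **none** | **none** | stop |
| >3–5 | >2 | ALP <2, no hemolysis | 1 | stop | stop | stop |
| >3–5 | >2 | ALP ≥2 or hemolysis | 1 | **none** | **none** | stop |
| >1–3 | >2 | either | 2 | **none** | stop | stop |
| ≤1 | >2 | either | 2 | stop | stop | stop |

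**Result.**

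- Reading A stops 2 + 1 + 1 + 2 = 6 of 12, leaving 6 uncovered.
- Reading B stops 2 + 2 + 1 + 1 + 2 + 2 = 10 of 12, leaving 2 uncovered.
- With the two conditions deleted, all 12 stop. No class outside the 12 gains a stop, because every route to a stop then needs ALT/AST >5 or bilirubin >2.

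**Worked profiles, ALP 1 and no hemolysis unless stated.**

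- Reading A: ALT 6 with bilirubin 0.8 stops; ALT 6, or even 20, with bilirubin 1.9 does not.
- Reading A: bilirubin 2.5 with ALT 0.8 stops; bilirubin 2.5 with ALT 2.9 does not.
- Readings A and B: ALT 6 with bilirubin 2.5 and ALP 1 stops as Hy's law; the same values with ALP 2.5 meet none of the three rules.

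**Other definitions of increase.** Cut-offs of >1.5, >2 and >3 x ULN for both tests were also tried. The gap narrows but never closes: ALT 4 with bilirubin 2.5 and ALP 2.5 is uncovered under every definition.

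**Raised baseline.** Section 4.2 excludes total bilirubin only from 1.5 x ULN, and allows a history of Gilbert's syndrome if direct bilirubin is not above ULN. On reading A, a subject enrolled with bilirubin between 1 and 1.5 x ULN has the ALT/AST stop disabled from the start. The adjusted Hy's law thresholds in Section 8.4.1 still require bilirubin to rise from that baseline.

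**The case against.** The strongest reply is that the three bullets are evidently meant as two isolated-elevation rules plus one combined rule, so reading B is the natural one. On that reading only the corner with ALP at least 2 times ULN or hemolysis is open. This is fair: four of the six uncovered classes depend on reading A. But the text does not say so, and reading B still leaves a gap.

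The count also depends on the grid. Splitting by ALP and hemolysis counts two of the uncovered ALT-by-bilirubin regions twice, although that split makes no difference there. The documents give no frequency for any of these profiles. Both points stand; 6 of 12 describes the rule, not a risk.

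Some hemolysis cases would stop under the separate hemoglobin rule in Section 3.3 (below 10 g/dL). That covers hemolysis only when it is severe enough, and does nothing for raised ALP.

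There are also safeguards outside the three rules:

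- The uncovered values lie outside the Section 4.2 laboratory limits (the Gilbert's allowance aside), so at MAD entry they go to a joint investigator and sponsor decision.
- Section 8.4.1 asks for closer monitoring above 3 times ULN and sponsor review of uncertain Hy's law cases.
- Section 3.3 stops dosing for a serious adverse event on active treatment unless clearly unrelated.
- Section 6.4 allows withdrawal for safety.
- Section 3.2 requires chemistry review before escalation and lets escalation stop for "Other findings that, at the discretion of the study team and investigator, indicate that dose escalation should be halted".

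These reduce the risk, but none is a stop triggered by the values. Section 8.4.1 makes serious-event reporting automatic only for cases that meet the Hy's law laboratory criteria, which the uncovered cases do not.

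Finally, remaining exposure is limited. Most healthy cohorts are complete, adverse events so far were mild, Section 1.2.4 judged the animal liver enzyme changes not adverse, and the psoriasis cohorts have their own unconditional stops. That bears on urgency, not on whether the rule is right.

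**Conclusion.** The concern holds. As written, Section 3.3 leaves some combined liver elevations without an automatic liver stop although a milder profile would stop dosing. With normal baseline values, 6 of the 12 threshold-crossing classes are uncovered if *increase* means above ULN, and 2 of 12 if it means the Hy's law cut-offs. The part that survives both readings is ALT/AST above 3 times with bilirubin above 2 times ULN and either ALP at least 2 times ULN or hemolysis, apart from hemolysis that brings hemoglobin below 10 g/dL. How often a subject would fall there cannot be estimated from the documents. Discretionary cover and the clean record so far keep this below a critical defect, but it is an error in a safety rule of a first-in-human study with its highest MAD dose still to be given, and it should be fixed.

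**What to change.** In Section 3.3, delete the two conditions about the other test. Dosing would then stop for confirmed ALT/AST above 5 times ULN whatever the bilirubin, for confirmed bilirubin above 2 times ULN whatever the ALT/AST, or for Hy's law. The 50% criterion in Section 3.2 and the MAD-entry bar in footnote b need no edit, because both already refer to the stopping rules. The result has the same unconditional form as the psoriasis stops in Section 3.4.

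The cost is two phrases in one section, with no new tests or visits. A few more subjects may meet a stop, all of them with ALT/AST above 5 times or bilirubin above 2 times ULN. Defining *increase* as the Hy's law cut-offs instead would be a weaker repair, since it leaves the ALP and hemolysis corner open.
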